Appendix 7. Classification of Contraceptive Methods

Women of childbearing potential must use either 1 highly effective method of contraception or a combination of 2 effective methods of contraception. The patient may choose to use a double-barrier method of contraception (see chart below).

- Barrier protection methods without concomitant use of a spermicide are not an effective or acceptable method of contraception. Thus, each barrier method must include use of a spermicide (that is, condom with spermicide, diaphragm with spermicide, female condom with spermicide). It should be noted, however, that the use of male and female condoms as a double-barrier method is not considered acceptable due to the high failure rate when these barrier methods are combined.

Methods of Contraception

Highly Effective Methods of Contraception	Effective Methods of Contraception (must use combination of 2 methods)

 • Combined oral contraceptive pill and mini-pill • NuvaRing® • Implantable contraceptives • Injectable contraceptives (such as Depo-Provera®) • Intrauterine device (such as Mirena® and ParaGard®) • Contraceptive patch – ONLY women <198 lb or 90 kg • Total abstinence • Vasectomy 	
 • Male condom with spermicide • Female condom with spermicide • Diaphragm with spermicide • Cervical sponge • Cervical cap with spermicide

**Appendix 8. Insulin Lispro Antibody Follow-Up
Assessment**

Rationale for Insulin Lispro Antibody Follow Up Assessment

As requested by the US FDA, any patient who develops a treatment-emergent anti-insulin lispro antibody (TEADA) response at any time during the study that has not returned to baseline by the completion of Visit 801 should undergo follow-up for antibodies to insulin lispro. Specific thresholds for determining treatment-emergent and return-to-baseline will be specified and documented in the SAP after being agreed with the FDA. Data collected during the insulin lispro antibody follow-up period is intended to evaluate whether antibodies to insulin lispro return to the prespecified baseline range and, in cases where antibodies remain elevated, to assess the possibility of loss of efficacy that may result from insulin neutralizing antibodies.

Eligibility for Insulin Lispro Antibody Follow-Up Assessment

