6.12.7.1. Treatment Emergent Anti-Insulin Lispro Antibody

The treatment-emergent anti-insulin lispro antibody (denoted as treatment-emergent antidrug antibody [TEADA] throughout this SAP) is based on the change from baseline (Visit 2) to postbaseline (post-Visit 2) in the anti-insulin lispro antibody level (percent binding). Treatment-emergent antidrug antibody can be sub-classified as either treatment-induced (not detected anti-insulin lispro antibody at baseline) or treatment-boosted (detected anti-insulin antibody at baseline):

- treatment-induced response: change from not detected anti-insulin lispro at baseline (Visit 2) to postbaseline detected anti-insulin lispro;
- treatment-boosted response: change from detected anti-insulin lispro at baseline (Visit 2) to postbaseline detected anti-insulin lispro antibody level (percent binding) at least 157% of the baseline value.

The TEADA status during a specific analysis period will be determined using all data in the corresponding analysis period regardless of IP use. The summary for TEADA status and the anti-insulin lispro antibody level will use the same analysis data.

The number and percentage of patients with positive TEADA response during the treatment period of 0 to 26 weeks will be summarized by treatment group. For patients with positive TEADA response during the treatment period of 0 to 26 weeks, the number and percentage of patients with positive insulin cross-reactivity anytime during the treatment period of 0 to 26 weeks will also be summarized by treatment group. Treatment groups will be compared by Fisher's exact test.

The above summary of TEADA response will be repeated for the analysis period of Visit 2 to Visit 801. The 2 double-blind treatment groups and the open-label treatment group will be summarized separately due to different duration of treatment period. For patients with positive TEADA response, the number and percentage of patients not meeting the TEADA criteria at Visit 801 will also be summarized.

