6.12.7.2. Anti-Insulin Lispro Antibody Return to Baseline

Any patient who develops a TEADA response at any time during the treatment period (0 to 52 weeks for double-blind treatment groups and 0 to 26 weeks for open-label treatment group) that has not returned to baseline at Visit 801 should undergo follow-up for antibodies to insulin lispro for a maximum of 6 months after Visit 801 or until anti-insulin lispro antibodies return to baseline range, whichever occurs sooner. The analyses for return to baseline will only include patients meeting this antibody follow-up entry criteria. Return to baseline (RBL) is defined as

- not detected postbaseline anti-insulin lispro antibody level at or after Visit 801 for patients with not detected status at baseline, or
- the detected postbaseline anti-insulin lispro antibody level (percent binding) at or after Visit 801 is less than 157% of the baseline value for patients with detected status at baseline.

Reasons for discontinuation from the antibody follow-up at Visits 802 and 803 will be summarized by the randomized treatment groups. No treatment comparison will be conducted.

Duration of exposure to IP will be summarized by treatment groups. Only descriptive statistics: n, mean, SD, median, minimum, maximum, and sum (that is, total patient-years of exposure), will be provided.

The number and percentage of patients whose anti-insulin lispro antibody levels meet the RBL criteria will be summarized by visit (Visit 802, and 803).

For the patients participating in the insulin antibody follow up, a summary of HbA1c, the insulin dose (prandial, basal, and total daily insulin dose), vital signs, body weight, AEs and concomitant medications reported during the immunogenicity follow up period will be summarized by randomized treatment group. The summary will include descriptive statistics and no statistical test will be performed for treatment comparison.

A scatter plot using the antibody percent binding at the last visit in the immunogenicity follow up period as X-axis and the HbA1c value at the same visit as Y-axis will be generated. A similar scatter plot with total daily dose as Y-axis will also be generated.

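### The antibody return-to-baseline rule omits patients who were detected at baseline and later become not detected, so read literally it counts cleared antibody as not returned

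*SAP*

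**What the plan says.** The protocol does not set the threshold itself. Its Appendix 8 (rationale for the antibody follow-up) says: "Specific thresholds for determining treatment-emergent and return-to-baseline will be specified and documented in the SAP after being agreed with the FDA". The SAP wording therefore governs.

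SAP section 6.12.7.2 gives two limbs for return to baseline. The first is "not detected postbaseline anti-insulin lispro antibody level at or after Visit 801 for patients with not detected status at baseline, or" the second, which reads "the detected postbaseline anti-insulin lispro antibody level (percent binding) at or after Visit 801 is less than 157% of the baseline value for patients" whose baseline sample was detected.

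SAP section 6.12.7.1 defines a treatment-emergent antibody response (TEADA) in two forms. Treatment-induced is "change from not detected anti-insulin lispro at baseline (Visit 2) to postbaseline detected anti-insulin lispro". Treatment-boosted starts from a detected baseline and needs a "postbaseline detected anti-insulin lispro antibody level (percent binding) at least 157% of the baseline value". For patients with a positive response, that section adds that "the number and percentage of patients not meeting the TEADA criteria at Visit 801 will also be summarized".

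Return to baseline has three uses in section 6.12.7.2:

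- **Entry.** Patients with a response that has not returned at Visit 801 go into follow-up, and "The analyses for return to baseline will only include patients meeting this antibody follow-up entry criteria".
- **Stopping.** Follow-up runs "for a maximum of 6 months after Visit 801 or until anti-insulin lispro antibodies return to baseline range, whichever occurs sooner".
- **Reporting.** The number and percentage meeting the rule are summarised at Visits 802 and 803.

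**The concern.** The second limb makes detection at the later visit a condition of having returned. A patient with antibody at baseline, a boosted response on treatment, and no detectable antibody at Visit 801 or later has the most complete resolution possible, yet meets neither limb.

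The follow-up exists, at the FDA's request, to evaluate whether antibodies come back to the baseline range (Protocol Appendix 8). A rule that leaves out complete clearance makes that percentage too low. It could also ask patients with no detectable antibody to attend up to two further visits, 802 and 803, over about 26 weeks.

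**Working it through.** The plan gives no figure to reproduce; this is a check of a definition. Let *b* be percent binding at Visit 2 and *p* percent binding at a later visit, with ND for not detected.

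- **TEADA criteria at a visit** (SAP 6.12.7.1): *b* is ND and *p* is detected; or both are detected and *p* ≥ 1.57 × *b*.
- **Return to baseline** (SAP 6.12.7.2): both are ND; or both are detected and *p* < 1.57 × *b*.

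Every combination, with the rules as written and with the second limb corrected:

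| Baseline | Later visit | Meets TEADA criteria | Returned, as written | Returned, corrected |
|---|---|---|---|---|
| ND | ND | no | yes | yes |
| ND | detected | yes | no | no |
| detected | detected, below 157% | no | yes | yes |
| detected | detected, 157% or more | yes | no | no |
| detected | ND | no | **no** | yes |

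In the first four rows, return to baseline is the exact complement of the TEADA criteria. Only the last row breaks the pattern.

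**Example.** Take baseline binding of 10% (illustrative). The cut-off is 1.57 × 10 = 15.7%. A later value of 15% is 15/10 = 150% of baseline, so the patient has returned. A later value of 30% is 300%, so the patient has not. A later result of not detected has not returned either, although it is the lowest result possible.

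**Can the number alone close the gap?** Not safely. Protocol section 9.8.1 says the assay gives a percent-binding value for positive samples, so a not-detected sample may have no value to compare with 157% of baseline.

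**Who is affected.** A patient detected at baseline can have a TEADA response only by the boosted route. The affected patients are therefore those with a boosted response during treatment who are later not detected. They fall into two groups:

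- *c₁*: not detected at Visit 801. As written they enter follow-up and the analysis set; corrected, they do not enter.
- *c₂*: properly in follow-up at Visit 801, then not detected at Visit 802 or 803. As written they are not counted as returned and do not meet the stopping rule; corrected, they do.

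Let *N* be the correct analysis set and *R* the number correctly returned at a visit. Assume the *c₁* patients stay not detected and attend. The correct proportion is *R/N*; the literal rule gives (*R* − *c₂*)/(*N* + *c₁*). Either group lowers the reported proportion (provided *R* is above zero). The documents give neither count, so no percentage can be put on it.

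**The case against.** **Intent.** The strongest reply is that nobody would apply the rule this way. Protocol Appendix 8 describes the follow-up as concerned with antibodies that remain elevated or persist, and has some later samples tested only when the previous result was above baseline. A not-detected result in a baseline-positive patient is none of these, and a programmer may well treat it as returned. This stands as evidence of intent. It does not repair the definition: the protocol leaves the thresholds to the SAP, the SAP makes detection an explicit condition, and no other section deals with the cleared state.

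**Importance.** Antibody incidence is a tertiary/exploratory objective (objective 18). The return-to-baseline outputs are counts and percentages with no planned treatment test. The by-visit listing in SAP 6.12.7.1 shows detection status and percent binding, so a misclassified patient could be found. All of this stands, and it keeps the point small.

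A reader might infer more than the documents support:

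- *That cleared patients will in fact be kept in follow-up.* This holds only if sites are notified on the literal rule; the documents do not state that outcome.
- *That two competing resolution percentages are planned at Visit 801.* They are not. The return-to-baseline percentage is reported at Visits 802 and 803; the planned Visit 801 summary uses the TEADA criteria and already treats a cleared patient as resolved. The inconsistency is between that summary and the entry condition applied to the same sample.
- *That the follow-up scatter plots would show these patients as persistent.* The plots use percent binding, not return-to-baseline status. A not-detected patient would have a low value or none.

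**Conclusion.** The gap is certain on the text: one of five baseline-by-later states is unassigned and falls by default to not returned. The classification is wrong for every patient in that state if the rule is applied literally.

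Its reach is narrow. It affects only patients with a treatment-boosted response who later become not detected. It bears only on entry to and stopping of antibody follow-up and on the descriptive counts at Visits 802 and 803. The number of patients is unknown and may be small, and nothing in the documents supports an estimate of the understatement. No primary, multiplicity-adjusted or other secondary objective is affected. The conclusion assumes only that the SAP definition is used as worded.

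**What to change.** Reword the second limb of the definition in SAP section 6.12.7.2:

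> For patients with detected status at baseline, the postbaseline antibody at or after Visit 801 is not detected, or is detected at less than 157% of the baseline value.

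The 157% threshold is unchanged and only the detected-to-not-detected state moves. Return to baseline then becomes the exact complement of the visit-level TEADA criteria, so section 6.12.7.1 needs no change.

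The cost is one phrase in the SAP and the matching program condition, applied also wherever results are turned into notifications to sites. Because the thresholds were to be agreed with the FDA, the sponsor should check that the rewording matches that agreement. Relative to the literal rule, the change can only reduce the number of follow-up visits.

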6.12.8. Patient Narratives

Patient narratives will be provided for all patients in the study who experience any of the following “notable” events prior to data cutoff for the submission:

- deaths
- serious adverse events
- discontinuations from study (or study drug) due to AEs
- pregnancy

A list of patients who meet the criteria for narratives will be provided.

6.13. Subgroup Analyses

6.13.1. Subgroup Analyses for HbA1c

The following subgroups will be analyzed for HbA1c if there are sufficient numbers of patients per group (for example, at least 10% in each group) using data collected from all randomized patients prior to discontinuation of IP through Week 26:

- age (<40, ≥40 years)
- hemoglobin A1c stratum (≤7.5% vs. >7.5%)
- patient's personal CGM/FGM use during the study (Yes vs. No)
- sex (male vs. female)
- body mass index (<25 vs. ≥25, and <30 vs. ≥30 kg/m²)
- duration of diabetes (using the median as the cut-off)
- race
- ethnicity
- country
- region (Europe, North America, Eastern Asia [Japan, Taiwan, Korea], and Other [India, Mexico, Argentina, Australia, New Zealand])
- baseline 1-hour PPG excursion (≤ baseline median, > baseline median)
- baseline 1-hour PPG (PPG ≤180 mg/dl, >180 mg/dl)
- baseline 2-hour PPG excursion (≤ baseline median, > baseline median)
- baseline 2-hour PPG (PPG ≤180 mg/dl, >180 mg/dl)
- type of basal insulin during the lead-in period (glargine U-100 vs. degludec U-100)
- prandial insulin dosing plan (carbohydrate counting or pattern adjustment)

Analyses for HbA1c and change from baseline in HbA1c will be performed using an MMRM model that includes the same fixed effects given for the primary analysis model plus factors of subgroup, 2-way interaction of subgroup and treatment, 2-way interaction of subgroup and visit, and 3-way interaction of treatment, visit and subgroup. The interaction of subgroup and treatment at the primary endpoint (Week 26) will be evaluated to assess the treatment by subgroup interaction. When analyzing HbA1c stratum as a subgroup the baseline HbA1c will not be included as a covariate to avoid confounding. The subgroup interaction effect will be evaluated using a significance level of 0.10, unadjusted.

Additional subgroup analyses may also be performed.

6.13.2. Subgroup Analyses for Hypoglycemic Events

For the documented symptomatic hypoglycemia based on the thresholds of blood glucose ≤ 70 mg/dL, the following subgroups will be analyzed using data collected from all randomized patients prior to discontinuation of IP through Week 26:

- age (<40 , ≥ 40 years)
- hemoglobin A1c stratum ($\leq 7.5\%$ vs. $>7.5\%$)
- region
- type of basal insulin during the lead-in period (glargine U-100 vs. degludec U-100)
- prandial insulin dosing plan (carbohydrate counting or pattern adjustment)
- patient's personal CGM/FGM use during the study (Yes vs. No)

The event rate and incidence will be analyzed using the same model specified in [Table 6.6](#) with the addition of factors for subgroup, and 2-way interaction of subgroup and treatment. The 2-way interaction will be used to evaluate treatment by subgroup interaction.

6.14. Interim Analyses and Data Monitoring

No interim analyses are planned for this study. If an unplanned interim analysis is deemed necessary, the appropriate Lilly medical director, or designee, will be consulted to determine whether it is necessary to amend the protocol.

The primary database lock will occur after all patients in the double-blind arms have either completed the Week 26 visit or discontinued from the study prior to Week 26, and after all patients in the open-label treatment group have completed Visit 801 (not including patients in Japan who will remain in the study through Week 52 before going to Visit 801). Investigators and patients will remain blinded to treatment assignments until the final database lock after all patients complete the study.

6.15. Clinical Trial Registry Analyses

Additional analyses will be performed for the purpose of fulfilling the Clinical Trial Registry (CTR) requirements.

Analyses provided for the CTR requirements include the following:

- Summary of AEs, provided as a dataset which will be converted to an XML file. Both Serious Adverse Events and 'Other' Non-Serious Adverse Events are summarized by treatment group and MedDRA PT.
- An AE is considered 'Serious' whether or not it is a TEAE.
- An AE is considered in the 'Other' category if it is both a TEAE and is not serious. For each Serious AE and 'Other' AE, for each term and treatment group, the following are provided:
 - the number of participants at risk of an event

- the number of participants who experienced each event term
 - the number of events experienced.
- For each Serious AE, these additional terms are provided for EudraCT:
 - the total number of occurrences causally related to treatment
 - the total number of deaths
 - the total number of deaths causally related to treatment.
- Consistent with www.ClinicalTrials.gov requirements, ‘Other’ AEs that occur in fewer than 5% of patients/subjects in every treatment group may be excluded if a 5% threshold is chosen. Allowable thresholds include 0% (all events), 1%, 2%, 3%, 4%, and 5%.
- Adverse event reporting is consistent with other document disclosures for example, the CSR, manuscripts, and so forth.

7. Unblinding Plan

The blinding and unblinding plan will be provided in a separate document stored in the Trial Master File.

8. References

- Computational Science Symposium Development of Standard Scripts and Programming Working Group. Analyses and Displays Associated with Measures of Central Tendency. Focus on vital Sign, Electrocardiogram, and Laboratory Analyte Measurements in Phase2-4 clinical Trials and Integrated Submission Documents. October 2013. Available at: http://www.phusewiki.org/docs/CSS%20White%20Papers%202016/CSS_WhitePaper_CentralTendency_v1.0.pdf. Accessed March 21, 2018.

Appendix 1. Empirical Estimation of Relative Event Rate

Traditionally, Poisson distribution has been assumed to draw inference for the rate of rare events. When the event is rare and the sample size is large, it is known that the overall number of events is approximately from Poisson distribution. However, for some not very rare events such as severe hypoglycemic events in T1D patients, the total number of events may not be distributed from Poisson and may be over-dispersed. Assuming Poisson distribution may significantly underestimate the variance, and therefore may reduce the coverage probability and inflate the Type-I error. An empirical method in estimating the variance of the relative event rate without assuming any distribution on the number of events will be provided in this appendix.

Let X_{ij} denote the count response variable for patient j in treatment group i . Let $Y_i = \sum_j X_{ij}$ be the total number of events for treatment group i , and T_i denote the exposure for treatment group i . Let $i = 0$ for the control group and $i = 1$ for the experimental treatment group. The event rate for treatment group i can be calculated as

$$\hat{r}_i = \frac{Y_i}{T_i}$$

The empirical variance of \hat{r}_i is

$$\widehat{Var}(\hat{r}_i) = T_i^{-2} \widehat{Var}(Y_i) = T_i^{-2} n_i S_i^2,$$

where S_i^2 is the variance of X_{ij} for treatment group i . Using the delta-method, the variance of $\log(\hat{r}_i)$ can be estimated as

$$\widehat{Var}(\log(\hat{r}_i)) = Y_i^{-2} n_i S_i^2$$

The relative rate of the experimental treatment versus the control treatment is estimated as

$$\hat{\lambda} = \frac{\hat{r}_1}{\hat{r}_0}$$

The variances of $\hat{\lambda}$ and $\log(\hat{\lambda})$ are

$$\widehat{Var}(\hat{\lambda}) = \hat{\lambda}^2 \widehat{Var}(\log(\hat{\lambda}))$$

$$\widehat{Var}(\log(\hat{\lambda})) = \widehat{Var}(\log(\hat{r}_0)) + \widehat{Var}(\log(\hat{r}_1)) = Y_0^{-2} n_0 S_0^2 + Y_1^{-2} n_1 S_1^2$$

Assuming $\log(\hat{\lambda})$ is asymptotically from a normal distribution, the $100(1 - \alpha)\%$ confidence interval for $\log(\hat{\lambda})$ can be constructed as

$$\left[\log(\hat{\lambda}) - z_{1-\frac{\alpha}{2}} \sqrt{\widehat{Var}(\log(\hat{\lambda}))}, \log(\hat{\lambda}) + z_{1-\frac{\alpha}{2}} \sqrt{\widehat{Var}(\log(\hat{\lambda}))} \right]$$

Then, the $100(1 - \alpha)\%$ confidence interval for $\hat{\lambda}$ is

$$\left[\hat{\lambda} \exp\left(-z_{1-\frac{\alpha}{2}}\sqrt{\widehat{Var}(\log(\hat{\lambda}))}\right), \quad \hat{\lambda} \exp\left(z_{1-\frac{\alpha}{2}}\sqrt{\widehat{Var}(\log(\hat{\lambda}))}\right) \right] \quad (1)$$

The p-value for testing the null hypothesis of $H_0: \lambda = 1$ is calculated as

$$p = 2\Phi\left(|\log(\hat{\lambda})|/\sqrt{\widehat{Var}(\log(\hat{\lambda}))}\right) \quad (2)$$

